**Time Line: Phase I Unilobar Disease**

CONFIDENTIAL

This material is the property of the University of Pennsylvania. Do not disclose or use except as authorized in writing by the study sponsor

**Timeline Unilobar HCC**

For patients with unilobar HCC, duration of HCQ therapy, frequency/timing of laboratory assessments, and definition of DLTs will be the same as with bilobar HCC. However, imaging, response assessment to initial TACE and phone call or clinical office visit following initial TACE will be performed at calendar Week 7. Repeat chemo-embolization may be performed at calendar Week 8 on HCCs with less than PR by mRECIST (see Imaging Assessment of Response under Section 3.3) or new HCCs which have developed since the initial TACE so long as LFTs are below the threshold of dose limiting toxicity. Subsequent follow-up clinic visits and imaging will be the same as with bilobar HCC - 3 months (+/- 1 week) and 6 months (+/- 1 week) following the last clinic visit.

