TACE will be performed using standard method currently employed by IR at HUP(41). In brief, following access to the arterial system, selective diagnostic arteriography of the superior mesenteric and celiac arteries will be performed to define the hepatic vasculature. Selective catheterization of arteries supplying the HCC will be performed, and a chemoembolic emulsion consisting of 50 mg of doxorubicin (Adriamycin; Pharmacia-Upjohn, Kalamazoo, MI) and 10 mg of mitomycin C (Bedford Laboratories, Bedford, Ohio) dissolved in 10 mL of water-soluble contrast material emulsified with ethiodized oil (Lipiodol, Guerbet Laboratories) will be administered. This is followed by embolization with 100-300 micron Embospheres (Merit Medical Systems, Inc, South Jordan, UT) until arterial blood flow to the tumor is substantially reduced (pruned tree appearance on post-embolization arteriography). Embolization with bland particles prior to administration of chemoembolic emulsion may be performed in cases of hepatic artery to portal venous shunting. Following TACE, the patient will be admitted overnight for intravenous hydration, prophylactic antibiotics, and pain control as routinely performed at HUP(41). As part of routine TACE procedure, patients will receive prophylactic antibiotics against gram negative and anaerobic organisms prior to the start of TACE and to be continued orally for 3 days following the procedure to minimize risk for hepatic abscess(41).

Two weeks after initial TACE (Week 6), patients will undergo repeat laboratory evaluation with CBC, CMP and PT/INR. The patient will be contacted the week after of receiving these laboratory results to assess for toxicity/AEs. Subsequently, patients will undergo TACE of the contra-lateral lobe at Week 8 if LFTs are below the threshold of dose limiting toxicity.

[figure not shown]

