**Phase I: Dose Escalation using “3+3” Cohort Expansion Design**

After initiating HCQ, dose limiting toxicity will be defined as events occurring at any time from initiation of HCQ (Week 0) up to Week 12. All patients who receive at least one day of HCQ will be included in the toxicity analysis.

DLT definition:

Toxicities will be graded according to the Common Terminology Criteria of Adverse Events (CTCAE) version 4.0. A DLT will be defined as one or more of the following occurring any time during the defined DLT period from initiation of HCQ (i.e Day -42 to -28) to completion of HCQ therapy 4 weeks following second TACE (Day 56 to Day 63): (1) grade 3 or higher hepatobiliary complication, except hepatic pain; (2) grade 4 or higher hepatic pain; (3) grade 3 or higher abnormality of liver function tests including total bilirubin (i.e. >3x the upper limit of normal) and transaminases (i.e. >5x the upper limit of normal, the Hospital of the University of Pennsylvania defines normal transaminases as AST< 41 IU/L and ALT < 63 IU/L); (4) grade 3 or higher elevation of serum creatinine (i.e >3x baseline or >3x upper limit of normal); (5) grade 3 or higher increase in international normalized ratio (i.e. greater than 2.5x upper limit of normal or >2.5x baseline if anti-coagulated); or (6) any grade 3 or higher toxicity that is possibly or definitely related to treatment. Given the prevalence of baseline thrombocytopenia in patients with HCC, decreases in platelet count will not be evaluated as a DLT.

The initial dose of HCQ will be 400mg PO daily. If the initial dose of HCQ 400mg PO daily incurs DLT, the dose will be reduced to 200mg and an additional 3 patients will be enrolled at this level (see “3+3” Cohort Expansion chart below). If DLTs do not occur at HCQ 400mg PO daily, the dose will be escalated by 400mg increments to a maximally administered dose of HCQ 1200mg (administered as 600mg PO twice daily) with enrollment of each cohort dictated by the “3+3” design (see “3+3” Cohort Expansion and Dose Schema Charts below). The dose may be escalated to the next level once at least 3 patients at a particular HCQ dosage have been observed for 1 month after second TACE (i.e. day 56 to day 63).

“3+3” Cohort Expansion Design Decision Making Regarding Dose Escalation

“3+3” Cohort Expansion Design Decision Making Regarding Dose Escalation	
Number of Patients with DLT at a Given Dose Level	Escalation Decision Rule
0 out of 3	Escalate

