### 3.2 Primary Study Endpoints

#### Phase I:

The primary end points of Phase I are dose limiting toxicity and maximum tolerated dose. DLT, graded according to the Common Terminology Criteria of Adverse Events (CTCAE) version 4.0, will be defined as one or more of the following events occurring any time during the defined DLT period from initiation of HCQ (Week 0) to 1 month following second TACE (Week 12) excluding the day immediately following TACE: (1) grade 3 or higher hepatobiliary complication, except hepatic pain; (2) grade 4 or higher hepatic pain; (3) grade 3 or higher abnormality of liver function tests including total bilirubin (i.e. >3x the upper limit of normal) and transaminases (i.e. >5x the upper limit of normal, the Hospital of the University of Pennsylvania defines normal transaminases as AST < 41 IU/L and ALT < 63 IU/L); (4) grade 3 or higher elevation of serum creatinine (i.e >3x baseline or >3x upper limit of normal); (5) grade 3 or higher increase in international normalized ratio (i.e. greater than 2.5x upper limit of normal or >2.5x baseline if

CONFIDENTIAL

This material is the property of the University of Pennsylvania. Do not disclose or use except as authorized in writing by the study sponsor

anti-coagulated); or (6) any grade 3 or higher toxicity that is possibly or definitely related to treatment. Given the prevalence of baseline thrombocytopenia in patients with HCC, decreases in platelet count will not be evaluated as a DLT.

Prior investigations have demonstrated the safety of TACE for HCC with a reported rate of major complications related renal dysfunction, biliary injury, gastrointestinal tract ulcer, and treatment related mortality ranging between 2 and 3%(45). Rates of hepatic failure in multiple studies have averaged 7.5%(45).

Phase II:

The primary end point of Phase II will be rate of complete imaging response by mRECIST (see Imaging Assessment of Response under Section 3.3).

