### **6.7 Week 8:**

Patients with **bilobar disease** will undergo TACE of the contra-lateral lobe to treat additional HCC. This second session of TACE will be performed only if the patient's clinical status and laboratory assessments have returned to baseline and the patient has not had any dose limiting toxicity.

Patients with **unilobar disease** will undergo an IR clinical office visit. At the clinical office visit - compliance with HCQ therapy, toxicity and AEs will be recorded. In order to determine if a second session of TACE is needed for subjects, a response assessment with imaging (contrast enhanced MRI or CT) will also be conducted at this visit.

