### **6.8 Week 10:**

Patients with **bilobar disease** and patients with **unilobar disease not undergoing a second session of TACE** will have laboratory assessments (CBC, PT/INR, CMP) to check for DLT.

Other patients with **unilobar disease** will undergo second session of TACE. This second session of TACE will be performed only if 1.) the HCC is less than PR by mRECIST or new HCC has developed since the initial TACE, 2.) the patient's clinical status and laboratory assessments have returned to baseline and 3.) the patient has not had any dose limiting toxicity.

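### Unilobar re-treatment is dated Week 8 in section 3.1 but Week 10 in section 6; at Week 10 the DLT end date contradicts itself, and section 6 lists no blood test after re-treatment until the 3-month visit

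*Combined protocol and SAP*

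**What the plan says.** Two schedules are given for a patient with unilobar disease who needs a second TACE.

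- Section 3.1, Timeline Unilobar HCC: response imaging at Week 7, then "Repeat chemo-embolization may be performed at calendar Week 8 on HCCs with less than PR by mRECIST" (or on new tumours). The same paragraph states that "frequency/timing of laboratory assessments, and definition of DLTs will be the same as with bilobar HCC".
- Section 6.7, under Week 8: "In order to determine if a second session of TACE is needed for subjects, a response assessment with imaging" takes place at that visit.
- Section 6.8, under Week 10, covers the second TACE in unilobar patients: "This second session of TACE will be performed only if 1.) the HCC is less than PR by mRECIST" (or new HCC has developed), laboratory values are back to baseline and there has been no DLT.

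The end of DLT observation is expressed both in words and in dates.

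- Section 3.1, dose escalation: DLTs are "events occurring at any time from initiation of HCQ (Week 0) up to Week 12". The DLT definition there then runs to the end of HCQ four weeks after the second TACE, equated with Day 56 to Day 63.
- Section 3.1, escalation rule: at least three patients must "have been observed for 1 month after second TACE (i.e. day 56 to day 63").
- Section 3.2: the period runs "from initiation of HCQ (Week 0) to 1 month following second TACE (Week 12").

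For bilobar patients, section 3.1 places blood tests two weeks after each session: "Two weeks after initial TACE (Week 6), patients will undergo repeat laboratory evaluation with CBC, CMP and PT/INR", and again at Week 10 after the Week 8 session. For re-treated unilobar patients, section 6 lists labs at Weeks 2 and 6. The Week 10 labs go only to bilobar patients and to unilobar patients without a second session (6.8). Nothing is required at Week 12 (6.9). Week 14 has imaging, an office visit and recording of toxicity, with no labs listed (6.10). Labs next appear at the 3-month follow-up (6.11).

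**The concern.** The two dates are different nominal schedules, and section 6 builds a separate Week 14 visit on its own version. The DLT window and the escalation clock carry calendar dates that match the section 3.1 version. A site that follows section 6 therefore has a DLT period whose words and dates point to different days, in the definition of the Phase I primary endpoint.

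DLT criteria 3, 4 and 5 (liver tests, creatinine, INR) can be met only if blood is drawn. A site following section 6 as written would not look for these events after re-treatment. The protocol itself treats this risk as important: section 8.3.4 makes liver or renal toxicity after the first TACE an adverse event of special interest.

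**Working it through.** **Inputs.** First TACE at Week 4 (6.4), taken as Day 0, so Day = (Week − 4) × 7. Unilobar second TACE at Week 8 (3.1) or Week 10 (6.8). Window end at Week 12, at Day 56 to 63, or 4 weeks / 1 month (28 days) after the second TACE (3.1, 3.2). HCQ stops at Week 12 or Week 14 (6.11). Assumption: 3 months = 13 weeks.

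**1. The protocol's own dates.** Second TACE at Week 8: (8 − 4) × 7 = Day 28. Adding 28 gives Day 56 = Week 12, as stated. To Day 63 it is 63 − 28 = 35 days. HCQ from Day −42 or −28 to Day 56 or 63 lasts 12 to 15 weeks, which matches the synopsis. The dates reproduce with a Week 8 session.

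**2. The same dates with section 6.8.** Second TACE at Week 10: (10 − 4) × 7 = Day 42.

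- By the words: 42 + 28 = Day 70 = Week 14.
- By the dates: 56 − 42 = 14 days and 63 − 42 = 21 days after the session.
- If that visit uses its full 14-day grace (section 6), the dates leave 0 to 7 days.

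**3. First listed lab after the second TACE.**

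| Pathway | Second TACE | Next listed lab | Gap |
|---|---|---|---|
| Bilobar (3.1, 6) | Week 8 | Week 10 | 10 − 8 = 2 weeks |
| Unilobar, 3.1 schedule with bilobar lab timing | Week 8 | Week 10 | 2 weeks |
| Unilobar, section 6 | Week 10 | 3-month visit: 12 + 13 = Week 25, or 14 + 13 = Week 27 | 15 or 17 weeks |

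With the ±1 week visit window, the last row is 14 to 18 weeks. Bilobar calendar timing applied to a Week 10 session puts the draw in Week 10, the week of the procedure.

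**4. Effect on the 3+3 rule.** Take three patients at a dose and one DLT in Week 13 in a patient re-treated at Week 10. Under the Week 12 limit the count is 0 of 3 and the dose escalates. Under one month after the second TACE it is 1 of 3 and three more patients enter. An event after Day 63 and by Day 70 lies outside every fixed date but inside the 28 days.

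**The case against.** A reader might infer that the window simply closes 14 to 21 days after a Week 10 session. The documents do not support that. The DLT definition and escalation rule in 3.1, and the endpoint in 3.2, also tie the end to four weeks or one month after the second TACE. The Week 14 visit in 6.10 and the Week 12 or Week 14 HCQ stop in 6.11 fit a Day 70 end with 28 days kept. Only the Week 12 limit opening the 3.1 dose-escalation text is unconditional. What stands is a conflict between words and dates with no rule for resolving it. The 14 to 21 days is also a nominal case: HCQ may start as early as Day −42, and a calendar Week 10 session is then Day 28. That does not reconcile the two schedules.

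A reader might also infer that no lab is required after re-treatment. Section 3.1 gives unilobar patients the bilobar lab timing. Counted from the TACE, that means a draw two weeks later; counted by calendar week, it means Week 10. The requirement is therefore conflicting rather than absent. The timeline figures are not in the copy reviewed and might show the draw.

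Safeguards exist. The Week 14 visit records toxicity, the medical monitor reviews records before escalation (8.6), and special-interest events are reported regardless of cause (8.3.4). Clinical DLTs can be found this way, but none of these steps creates a blood test. The background in 1.1 says liver-test rises mostly normalize within a week, so a Week 13 event is the less usual case. That makes the missing draw the larger part of the point.

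**Conclusion.** The point holds as an internal inconsistency that should be corrected, with medium confidence. Unilobar imaging and re-treatment are at Weeks 7 and 8 in section 3.1 and at Weeks 8 and 10 in section 6. At a nominal Week 10, the DLT end and escalation clock are either Day 70 or Day 56 to 63, and the protocol does not choose. Section 6 lists no blood test for about 15 to 17 weeks after re-treatment, against 2 weeks for bilobar patients, so DLTs under criteria 3 to 5 could be missed.

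This rests on the first TACE at Week 4, on 3 months as 13 weeks, and on the text of section 6 without the figures. Only re-treated unilobar patients are affected. Their share is not given, so the documents do not support any figure for a changed escalation probability or a wrong MTD. If Week 8 is the intended date and the stated Week 10 lab is drawn, both problems disappear.

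**What to change.** Choose one week for unilobar re-treatment and use it in section 3.1 and section 6, with the imaging week to match.

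- **If Week 10 is kept:** in 3.1 and 3.2, define the DLT window and the escalation clock as running through 28 days after the last TACE and at least to Week 12. The minimum covers patients with a single session. Replace the fixed dates accordingly. Add CBC, CMP and PT/INR at Week 12, two weeks after that session. Anchor the window to the TACE rather than to the HCQ stop: HCQ started at Day −42 reaches the 15-week cap at −42 + 105 = Day 63, before Day 70.
- **If Week 8 is chosen:** keep Week 12 as the end, move the section 6 visits to match, and list the Week 10 lab for re-treated unilobar patients.

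The cost is a protocol amendment, one blood draw per re-treated unilobar patient and, if Week 10 is kept, up to about two weeks' longer wait before escalation (70 − 56 = 14 days) when such a patient is in the cohort.

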**Phase I: Dose Escalation using “3+3” Cohort Expansion Design**

After initiating HCQ, dose limiting toxicity will be defined as events occurring at any time from initiation of HCQ (Week 0) up to Week 12. All patients who receive at least one day of HCQ will be included in the toxicity analysis.

DLT definition:

Toxicities will be graded according to the Common Terminology Criteria of Adverse Events (CTCAE) version 4.0. A DLT will be defined as one or more of the following occurring any time during the defined DLT period from initiation of HCQ (i.e Day -42 to -28) to completion of HCQ therapy 4 weeks following second TACE (Day 56 to Day 63): (1) grade 3 or higher hepatobiliary complication, except hepatic pain; (2) grade 4 or higher hepatic pain; (3) grade 3 or higher abnormality of liver function tests including total bilirubin (i.e. >3x the upper limit of normal) and transaminases (i.e. >5x the upper limit of normal, the Hospital of the University of Pennsylvania defines normal transaminases as AST< 41 IU/L and ALT < 63 IU/L); (4) grade 3 or higher elevation of serum creatinine (i.e >3x baseline or >3x upper limit of normal); (5) grade 3 or higher increase in international normalized ratio (i.e. greater than 2.5x upper limit of normal or >2.5x baseline if anti-coagulated); or (6) any grade 3 or higher toxicity that is possibly or definitely related to treatment. Given the prevalence of baseline thrombocytopenia in patients with HCC, decreases in platelet count will not be evaluated as a DLT.

The initial dose of HCQ will be 400mg PO daily. If the initial dose of HCQ 400mg PO daily incurs DLT, the dose will be reduced to 200mg and an additional 3 patients will be enrolled at this level (see “3+3” Cohort Expansion chart below). If DLTs do not occur at HCQ 400mg PO daily, the dose will be escalated by 400mg increments to a maximally administered dose of HCQ 1200mg (administered as 600mg PO twice daily) with enrollment of each cohort dictated by the “3+3” design (see “3+3” Cohort Expansion and Dose Schema Charts below). The dose may be escalated to the next level once at least 3 patients at a particular HCQ dosage have been observed for 1 month after second TACE (i.e. day 56 to day 63).

“3+3” Cohort Expansion Design Decision Making Regarding Dose Escalation

“3+3” Cohort Expansion Design Decision Making Regarding Dose Escalation	
Number of Patients with DLT at a Given Dose Level	Escalation Decision Rule
0 out of 3	Escalate
$\geq 2$	Stop Dose Escalation 
 
• This dose exceeds the MTD
 
• Three additional patients will be entered at the next lowest dose level if only 3 patients were treated previously at that dose
 

1 out of 3	Enter 3 more patients at this dose level 
 
• If 0 of these 3 additional patients experience DLT, proceed with dose
 

CONFIDENTIAL

This material is the property of the University of Pennsylvania. Do not disclose or use except as authorized in writing by the study sponsor

	
escalation to the next level
 
 
• If 1 or more of these 3 additional patients experience DLT, then dose escalation is stopped. This dose level exceeds the MTD
 
• Three additional patients will be entered at the next lowest dose level if only 3 patients were treated previously at that level
 

≤1 out of 6 at the highest tolerable dose	This is considered the MTD. At least 6 patients must be enrolled at the MTD.

Table: Hydroxychloroquine Dose Escalation Schema

Dose level	HCQ
-1a	200 mg qday (9AM)
1	400 mg qday (9AM)
2	400 mg BID (9AM/9PM)
3	600 mg BID (9AM/9PM)

### Phase II: Effect of Combined Therapy on Complete Imaging Response using Simon’s Two Stage Design

Following determination of the MTD, a cohort of patients will be enrolled at the MTD to examine the benefit of combined HCQ and TACE therapy on complete response rate. In the reported literature, the rate of complete necrosis of HCC ranges from 29-43% even after repeated TACE(7,11,13-18). Georgiades, et al., studied the radiologic responses of 116 patients who underwent TACE(19). After a second TACE, the complete radiologic response rate increased from 14 to 38%. However, still over 25% of the patients did not respond at all to two TACE treatments, and 62% of patients did not have a complete response by imaging (see Imaging Assessment of Response under Section 3.3)(19).

This phase of the trial will use a Simon's optimal two-stage design. The null hypothesis that the complete response (CR) rate of TACE and HCQ will be similar to TACE alone ( $p_0 = 40\%$ ) will be tested against a one-sided alternative, the complete response (CR) rate of combined TACE and HCQ will be 60% ( $p_1$ ). In the first stage, 12 patients will be accrued, of which 6 will patients treated at the MTD from the Phase I trial. If there are 7 or fewer complete responses by mRECIST in these 16 patients, the study will be stopped. The probability of stopping the trial after the first stage of the Simon’s optimal design is 72%. Otherwise, 30 additional patients will be accrued for a total of 46 patients. The null hypothesis will be rejected if 23 or more responses are observed in 46 patients. This design yields a type I error rate of 0.05 and power of 0.80 when the complete response rate by mRECIST of combined TACE and HCQ is 60%.

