## Study Summary

Title	Phase I-II Clinical Trial of the Safety and Preliminary Efficacy of Hydroxychloroquine combined with Transarterial Chemoembolization in Unresectable Hepatocellular carcinoma
Short Title	Phase 1-2 Trial HCQ plus TACE in Unresectable HCC
Protocol Number	UPCC 22213
Phase	Phase 1-2
Methodology	Single arm, unblinded, dose escalation
Study Duration	5 years
Study Center(s)	Hospital of the University of Pennsylvania
Objectives	Primary Phase I: To determine dose limiting toxicities and maximum tolerated dose (MTD) of the oral administration of hydroxychloroquine (HCQ) in conjunction with transarterial chemoembolization (TACE) in treating hepatocellular carcinoma (HCC) Primary Phase II: To evaluate the tumor necrosis rate in a cohort of patients treated at the MTD
Number of Subjects	Maximum 58 [18 patients maximum (6 patients at 3 dose levels) to define maximum tolerated dose (MTD) and total of 46 patients as expansion of cohort at the MTD, which includes 6 patients at MTD from Phase I]
Diagnosis and Main Inclusion Criteria	≥18yo, unresectable HCC, outside transplant criteria Candidate for TACE for palliative therapy Exclusions: HCQ allergy, porphyria, uncontrolled psoriasis, and existing retinopathy
Study Product, Dose, Route, Regimen	Hydroxychloroquine: Initial Dose 400mg PO daily for 28 days prior to TACE and continued until 8 weeks (2mo) following initial TACE. Doses will be escalated to, 400 mg BID (9AM/9PM), and 600 mg BID ( 9AM/9PM) to define MTD.  Phase I: Dose escalation will be performed to define dose limiting toxicities and maximum tolerated dose (MTD) using 3+3 cohort expansion design.  Phase II: Expansion of cohort at MTD using Simon's optimal Two Stage design to define complete response rate as determined by mRECIST imaging criteria. Study will be powered to detect a 20% increase in complete response rate (i.e. complete necrosis) from 40% to 60%.
Duration of administration	12-15 weeks
Reference therapy	TACE without HCQ

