#### **Sample Size Determination and Power Calculation**

In the reported literature, the rate of complete necrosis of HCC ranges from 29-43% even after repeated TACE(9,13,15-20). Georgiades, et al., studied the radiologic responses of 116 patients who underwent TACE(21). After a second TACE, the complete radiologic response rate increased from 14 to 38%. However, still over 25% of the patients did not respond at all to two TACE treatments, and 62% of patients did not have a complete response by imaging (see Imaging Assessment of Response under Section 3.3)(21).

Using a Simon's optimal two-stage model, the efficacy of combined therapy at increasing complete imaging response rate will be tested. The null hypothesis that the complete response rate of TACE and HCQ will be similar to TACE alone ( $p_0 = 40\%$ ) will be tested against a one-sided alternative, the complete

CONFIDENTIAL

This material is the property of the University of Pennsylvania. Do not disclose or use except as authorized in writing by the study sponsor

response rate of combined TACE and HCQ will be 60% ( $p_1$ ). In the first stage, 16 patients will be accrued, of which 6 will be patients treated at the MTD in the phase I trial. If there are 7 or fewer complete responses in these 16 patients, the study will be stopped. The probability of stopping the trial after the first stage of the Simon's optimal design is 72%. Otherwise, 30 additional patients will be accrued for a total of 46 patients. The null hypothesis will be rejected if 23 or more responses are observed in 46 patients. This design yields a type I error rate of 0.05 and power of 0.80 when the complete response rate of combined TACE and HCQ is 60%.

Thus, the maximum number of patients needed to complete the trial will be approximately 58. If all 3 dose levels are investigated in the Phase I trial, 18 patients will be required. Forty patients will be needed to complete the Phase II component, of which 6 will be patients treated at the MTD in the Phase I trial.

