## 7.3 Subject Population(s) for Analysis and Duration of Study

Analysis of both primary and secondary end points will be performed on an intention to treat basis. A maximum of 58 patients will be required if all 3 dose levels are investigated in the Phase I trial. If 1-2 patients are enrolled per month, then we expect up to approximately 5 years will be needed to complete enrollment.

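### The Phase II sample sizes contradict each other (stage 1: 12 or 16; total: 40 or 46, each including 6 from Phase I), and the printed rejection count misses the stated type I error

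*Combined protocol and SAP*

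**What the plan says.** **Stage 1 size.** Section 3.1 (Phase II, Simon's two-stage design) says: "In the first stage, 12 patients will be accrued, of which 6 will patients treated at the MTD from the Phase I trial". The next sentence uses a different denominator: "If there are 7 or fewer complete responses by mRECIST in these 16 patients, the study will be stopped". It then continues: "Otherwise, 30 additional patients will be accrued for a total of 46 patients". Section 7.1 (Sample Size Determination and Power Calculation) says: "In the first stage, 16 patients will be accrued, of which 6 will be patients treated at the MTD in the phase I trial".

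**Phase II total.** The Study Summary gives a "total of 46 patients as expansion of cohort at the MTD, which includes 6 patients at MTD from Phase I". Section 7.1 also reaches 46 when it describes the two stages, but its last sentence reads: "Forty patients will be needed to complete the Phase II component, of which 6 will be patients treated at the MTD". The trial maximum is 58 in the Study Summary, in section 7.1 and in section 7.3: "A maximum of 58 patients will be required if all 3 dose levels are investigated in the Phase I trial".

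**Final test.** Sections 3.1 and 7.1 give the same rule: "The null hypothesis will be rejected if 23 or more responses are observed in 46 patients". Both attach to it a type I error of 0.05 and a power of 0.80 at a true complete response rate of 60%, against a null rate of 40%. Both put the probability of stopping after stage 1 at 72%.

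**The concern.** The stage 1 size decides when the futility look is taken. The Phase II total decides how many new patients are enrolled and is the denominator of the final rule. Each is given two values in current text, and no section says which governs. Section 8.5 makes failure in stage one a ground for ending the trial but repeats no number, so it relies on whichever section the reader opens.

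A team working from the accrual sentence in section 3.1 could hold the look 4 patients early (16 − 12). A team working from the last sentence of section 7.1 could close accrual 6 patients short (46 − 40).

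The same paragraphs also contain an error that needs no misreading to take effect. The printed rejection count does not deliver the error rates claimed for it. A trial that finished with exactly 23 responses would be declared positive under a rule whose type I error is above the stated 0.05.

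**Working it through.** **Inputs.** Null rate p0 = 0.40 and alternative p1 = 0.60, one-sided, type I error 0.05 and power 0.80 (sections 3.1 and 7.1). Futility if 7 or fewer responses; 30 patients in stage 2; rejection at 23 or more (same sections). Phase I maximum 18, of whom 6 carry over (Study Summary, section 7.1).

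**1. Reproduce the stated stopping probability.** Under p0 it is P(Bin(n1, 0.4) ≤ 7).
- n1 = 16: 0.716, which rounds to the stated 72%.
- n1 = 12: 0.943, which does not.

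**2. Add up the sizes.**
- 16 + 30 = 46, as stated; 12 + 30 = 42.
- 46 including 6 from Phase I: 40 new patients, maximum 18 + 46 − 6 = 58, as stated.
- 40 including 6 from Phase I: 34 new patients, maximum 18 + 40 − 6 = 52, which appears nowhere.

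So forty is the count of new patients (10 in stage 1 plus 30 in stage 2), wrongly described as including the 6.

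**3. Search for the design.** An exhaustive search over two-stage designs with N from 20 to 59, type I error at most 0.05 and power at least 0.80, minimising expected N under p0, returns: stop at 7 or fewer of 16, reject at more than 23 (24 or more) of 46. Expected N under p0 is 16 + (1 − 0.7161) × 30 = 24.5. The sizes 16 and 46 are therefore Simon's optimal design for these inputs.

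**4. Check the rejection count.** With stage 1 size n1, total N and rejection at R or more,

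P(reject) = Σ (x = 8 to n1) P(Bin(n1, p) = x) × P(Bin(N − n1, p) ≥ R − x).

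For n1 = 16, N = 46:

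| Reject at | Type I error (p = 0.4) | Power (p = 0.6) |
|---|---|---|
| 23 or more | 0.0770 | 0.829 |
| 24 or more | 0.0486 | 0.8006 |

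Only 24 or more matches the stated 0.05 and 0.80. In the optimal design 23 is the largest count that does not reject, so the text is off by one. Under the null, the chance of passing stage 1 and ending on exactly 23 is 0.0770 − 0.0486 = 0.0284.

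**5. What the wrong sizes would do.** These figures apply only if the printed cutoffs were carried over to the wrong sizes. At a true 60% rate, P(Bin(12, 0.6) ≤ 7) = 0.562, against P(Bin(16, 0.6) ≤ 7) = 0.142. Power, by the formula in step 4:

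| n1, N | Reject at 23 or more | Reject at 24 or more |
|---|---|---|
| 16, 46 | 0.83 | 0.80 |
| 12, 42 | 0.41 | 0.38 |
| 16, 40 | 0.65 | 0.55 |
| 12, 40 | 0.38 | 0.34 |

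None of the other size combinations gives the stated power with the printed rejection count.

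**The case against.** The strongest reply is that these are drafting slips that correct themselves. Wherever a decision rule is stated, its denominator is 16 or 46. No section states a rule at 12 or at 40. The 12 is contradicted by the sentence that follows it, and forty is the right count of new patients attached to the wrong clause. Every stated maximum is 58; 52 and 34 are inferences. The low power figures require staff to apply a rule worded for 16 or 46 patients to some other number.

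Much of this stands. The intended sizes can be recovered from the documents alone, no design stated in full has low power, and the figures in step 5 are conditional on misapplication. A total of 40 with the correct stage 1 would lower power but would not make failure the likelier result.

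It is also fair to say that 23 versus 24 is a different kind of error: the text is consistent on it, and changing it moves the decision boundary, so that edit is not merely clerical. But this argument does not rescue the paragraphs. The rejection count fails on the plain, intended reading of the sizes. And a prespecified single-arm trial should not leave its stage 1 size and total to be inferred from neighbouring sentences.

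**Conclusion.** The text is wrong as written on three figures: the stage 1 size in section 3.1 (12, should be 16), the description of the forty Phase II patients in section 7.1 (new patients, not a total that includes the 6), and the rejection count in both sections (23, should be 24). The first two are contradictions whose intended values can be recovered. The third changes the operating characteristics of the primary test: type I error is 0.077 rather than 0.05.

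The calculations are exact binomial. They assume the stated rates of 40% and 60%, the printed futility cutoff of 7, and that all patients counted, including the 6 from Phase I, share one response probability. This must be corrected, because these paragraphs define the primary hypothesis test and the trial's only numerical futility stop.

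**What to change.** - **Section 3.1:** change the stage 1 size from 12 to 16, made up of 6 patients from Phase I and 10 new ones.
- **Section 7.1, last sentence:** say that forty new patients are needed in addition to the 6 treated at the MTD in Phase I, 46 in total, so that 18 + 40 = 58.
- **Sections 3.1 and 7.1:** reject the null hypothesis at 24 or more responses in 46 patients, and quote the exact type I error (0.0486) and power (0.8006).

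The first two edits are clerical. The third is a change to the decision rule and should be identified as such in the amendment, which under section 11 goes to the ethics committee or IRB. It lowers power from 0.829 to 0.8006, still the level the plan claims. No patients are needed beyond the 58 already planned.
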